8.5 Expected Duration of Subject Participation

- Duration of physical patient participation will be:
 - Approximately 30 – 45 minutes to complete the informed consent process
 - Approximately 15 – 30 minutes to conduct interview 1
 - Approximately 15 – 30 minutes to conduct interview 2
 - Passive participation will continue until the global study is completed.

8.6 Adverse Events Reporting

- The Principal Investigator or delegate must report any Adverse Events (AE) from the time the subject signs the Informed Consent Form until the conclusion of the study-related activities. This study is not for diagnostic purposes, so if incidental health findings are discovered as part of a scan, these must be recorded on the AE log and the subject must be referred to their physician by the study PI ([name]).
- A Detailed Data Safety and Monitoring Plan (DSMP) has been included as an addendum to this protocol. The DSMP will comprehensively review AE, SAE, definitions, reporting procedures, and protocols.

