8.4.2 Trial Protocol for Default (i.e., Obligatory) TEE: Control Arm

- After induction, patients randomized to the default TEE trial arm will have the TEE probe passed into the esophagus after the endotracheal tube has been secured.
- The protocol for those enrolled in the default TEE trial arm will have one pre-surgical TEE exam (defined as ≥ 10 video acquisitions) and one post-surgical TEE exam (defined as ≥ 10 video acquisitions).
- While use (or lack of use) of TEE during isolated CABG surgery are both considered standard-of-care by national guideline recommendations, at the University of Pennsylvania, the typical practice is to place the TEE as a default monitor (i.e., immediately following induction of anesthesia and placement of the endotracheal tube). Therefore, for this pilot trial, this trial arm – the default/obligatory TEE – will be considered the control.

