8.4.3 Trial Protocol for As-Needed (i.e. Backup) TEE: Intervention Arm

- After induction of anesthesia, patients randomized to the as-needed TEE trial arm will not have the TEE probe placed after the endotracheal tube has been secured. However, both the TEE machine and TEE probe will both be present in the operating room to minimize any delay in probe placement if TEE is requested by the cardiac surgeon or deemed medically necessary by the cardiac anesthesiologist.
- As described above, because the typical practice at University of Pennsylvania is the obligatory placement of the TEE. Therefore, for this pilot trial, this trial arm – the as-needed/backup TEE – will be considered the intervention arm.

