10.1 Primary Endpoint Analysis

The goal of this RCT is to assess the real-world feasibility of undertaking a trial that will randomize isolated CABG surgery patients to default (i.e. obligatory) as-needed (i.e. backup) intraoperative TEE. Therefore, primary RCT endpoints are process-related. These include

1. Absolute subject recruitment
2. Number of TEEs performed in the as-needed TEE trial arm

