19.1 Data Safety and Monitoring Plan

19.1.1 Adverse Event (AE) and Serious Adverse Event (SAE) Collection and Reporting

19.1.1.1 Safety Monitoring Definitions and list of AEs and SAEs to be tracked

- (1) Adverse Event (AE) – Any untoward or unfavorable medical occurrence in a human subject, including any abnormal sign, symptom, or disease process, temporally associated with the subject's participation in the research, whether or not considered directly-related to the subject's participation in the research. The itemized list of adverse events we will track is provided in this section (subsection 5).
 - a. Clinically-significant but non-life threatening gastroesophageal complications possibly related to transesophageal echocardiography (TEE).
 - b. Cardiovascular complications after isolated CABG surgery.
 - c. Breach of confidentiality.
- (2) Serious Adverse Event (SAE) – Any AE that results in death or a life-threatening AE.
- (3) List of AEs and SAEs (severity of which will be assessed on a case-by-case basis)
 - a. Death
 - b. New myocardial infarction (MI) post-surgery
 - c. Unplanned post-surgery percutaneous coronary intervention (PCI)
 - d. Unplanned CABG surgery revision
 - e. Unplanned open valve repair or replacement
 - f. Stroke
 - g. Transient ischemic attack (TIA)
 - h. Return to operating room for bleeding
 - i. Cardiac tamponade
 - j. Pericardial effusion
 - k. Prolonged intubation (defined as >48 hours of mechanical ventilatory support)
 - l. Pneumonia
 - m. Surgical site infection
 - n. Unplanned ICD or pacemaker insertion post-surgery
 - o. Post-surgery angina
 - p. New-onset atrial fibrillation
 - q. Pulmonary embolism (PE)

Clinical Study Number:	NCT06154265	Document Title:	10/24/2024	Page 28 of 36
		Default vs As-Needed Intraoperative Transesophageal Echocardiography (TEE) in Low-Risk Isolated Coronary Artery Bypass Graft (CABG) Surgery: A Randomized Controlled Trial		

- r. Deep vein thrombosis (DVT)
 - s. Gastrointestinal or esophageal complication requiring diagnostic testing
 - t. Failed swallow evaluation

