- (3) Content of Data and Safety Monitoring Report: The written progress report submitted to the DSMB, UPenn IRB, NHLBI Program Officer will include: (a) trial status dates and checkpoints; (b) reports on data completeness; (c) logs of AEs/SAEs; (d) logs of changes to the trial protocol; (e) anticipated trial timeline and deadlines for trial deliverables.
- (4) DSMB Membership and Affiliation: DSMB members will be identified prior to start of the RCT. DSMB membership will be sent to the NHLBI. Should there be any questions regarding the independence of the DSMB, it will be addressed and corrected if necessary.
- (5) Conflict of Interest for DSMB: The DSMB should have no direct involvement with the study investigators or intervention. Each DSMB member will sign a Conflict of Interest Statement which includes current affiliations, if any, with pharmaceutical and biotechnology companies (e.g., stockholder, consultant), and any other relationship that could be perceived as a conflict of interest related to the trial and/or associated with commercial interest pertinent to RCT objectives.
- (6) Responsibilities of the DSMB:
 - a. Review the trial protocol, informed consent documents and plans for data safety and monitoring.
 - b. Evaluate the progress of the trial, including periodic assessments of data quality and timeliness, recruitment, accrual and retention, participant risk vs benefit, performance for the trials sites, and other factors potentially affecting study outcomes.
 - c. Consider factors external to the study when relevant information becomes available, such as scientific or therapeutic developments that may have an impact on the safety of the participants or the ethics of the trial.
 - d. Review study performance, make recommendations and assist in the resolution of problems reported by [name]
 - e. Protect the safety of the study participants.
 - f. Report to NHLBI on the safety and progress of the trial.

Clinical Study Number:	NCT06154265	Document Title:	10/24/2024	Page 31 of 36
		Default vs As-Needed Intraoperative Transesophageal Echocardiography (TEE) in Low-Risk Isolated Coronary Artery Bypass Graft (CABG) Surgery: A Randomized Controlled Trial		

- g. Make recommendations to the NHLBI and the PI ([name]) concerning continuation, termination or other modifications of the trial based on the observed beneficial or adverse effects of intraoperative TEE as proposed in the trial protocol.

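### Logging incidental scan findings as adverse events is expected to add AE-log entries in the default TEE arm through detection alone

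*Combined protocol and SAP*

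**What the plan says.** Section 8.6 requires that "if incidental health findings are discovered as part of a scan, these must be recorded on the AE log", and that the patient be referred to their physician. It makes no exception for a lesion that was already there and came to light only because a scan was done.

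Scanning differs by arm. Under section 8.4.2 each default-arm patient "will have one pre-surgical TEE exam (defined as ≥ 10 video acquisitions) and one post-surgical TEE exam", the second with the same minimum number of acquisitions. Under section 8.4.3, "patients randomized to the as-needed TEE trial arm will not have the TEE probe placed after the endotracheal tube has been secured"; TEE follows only on the surgeon's request or the anesthesiologist's judgement of medical necessity. How often that happens is itself a primary endpoint (section 10.1: "Number of TEEs performed in the as-needed TEE trial arm"), and no planning value is given.

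Section 10 has adverse events summarized in the final reports to NHLBI and NIH. Section 19.1.1.2 sends each AE or SAE to the DSMB for help with grading. Section 19.1.1.4 item (3) puts the AE/SAE logs in the reports to the DSMB, IRB and NHLBI. Item (6)g has the DSMB advise on continuing, stopping or modifying the trial "based on the observed beneficial or adverse effects of intraoperative TEE as proposed in the trial protocol". The list of tracked events in section 19.1.1.1 item (3) does not name incidental findings.

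**The concern.** An AE log supports a reading by arm only if events are ascertained alike in both arms. Here one route onto the log is the randomized exposure itself. The same silent lesion becomes an entry in a default-arm patient and goes unrecorded in an as-needed patient who is never scanned. Nothing in the plan separates such entries from harms before the log reaches the DSMB, the IRB, NHLBI and the final reports. In a trial this small, one or two extra entries can alter how a log looks, and here they would reflect the diagnostic yield of TEE rather than injury from it.

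**Working it through.** The plan states no AE rate, incidental-finding rate or expected as-needed TEE rate, so there is no figure to reproduce. The direction follows from the design; the size can only be illustrated.

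**Inputs**
- n per arm: 22 (section 10.3), or 11 if the n=22 in section 19.5.2 is a total split equally. The two sections disagree, so both are used.
- Share scanned, default arm: taken as 100% (section 8.4.2).
- Share scanned, as-needed arm: q, not stated; assumed 0 to 50%.
- Share of patients with a loggable finding: f, not stated; assumed 5%, 10% and 20%, equal in both arms. The scan in section 8.6 is taken to be TEE.

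**Formula, if scanned patients in both arms have the same finding rate**
- Expected default-arm entries = n × f
- Expected as-needed entries = n × f × q
- Expected excess = n × f × (1 − q)

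**Expected excess of default-arm entries**

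| n per arm | f | q=0% | q=10% | q=30% | q=50% |
|---|---|---|---|---|---|
| 22 | 5% | 1.10 | 0.99 | 0.77 | 0.55 |
| 22 | 10% | 2.20 | 1.98 | 1.54 | 1.10 |
| 22 | 20% | 4.40 | 3.96 | 3.08 | 2.20 |
| 11 | 5% | 0.55 | 0.49 | 0.39 | 0.28 |
| 11 | 10% | 1.10 | 0.99 | 0.77 | 0.55 |
| 11 | 20% | 2.20 | 1.98 | 1.54 | 1.10 |

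For example, at n=22 and f=q=10%: 22 × 0.10 = 2.20 entries against 22 × 0.10 × 0.10 = 0.22, an excess of 1.98. Treating the arms as independent binomials, the default arm shows more entries with probability 0.85 and the as-needed arm with probability 0.02. At n=11 the expected counts are 1.10 and 0.11, and the probabilities 0.64 and 0.03.

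**If as-needed patients are scanned for cause.** Let r be the finding rate among as-needed patients who are scanned. The excess becomes n × (f − q × r). At n=22 and f=q=10%:
- r=10%: 22 × (0.10 − 0.01) = 1.98
- r=20%: 22 × (0.10 − 0.02) = 1.76
- r=50%: 22 × (0.10 − 0.05) = 1.10
- r=100%: 22 × (0.10 − 0.10) = 0

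Selection for cause therefore shrinks the excess. For lesions equally common in both arms it cannot reverse it in expectation, because q × r cannot exceed f unless as-needed TEE detects more than the two protocol exams do.

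**After the change.** With incidental scan findings kept out of the AE count, their contribution to the excess is 0 at any f, q and r.

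**The case against.** The strongest reply is that the consequences are limited, and much of it stands.

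- **No by-arm AE test is planned.** AEs are summarized and sent as logs. The chi-squared and Wilcoxon sentence in section 19.5.1 concerns clinical data and does not mention the AE log. A reader might infer that a biased safety comparison passes into the future multicentre trial. The documents do not support that: the outcomes collected for planning it are the four in section 10.2, none of which counts incidental findings, and re-intervention there is already limited to the post-surgical period.
- **Entries are reviewed one by one.** Section 19.1.1.1 grades relatedness by whether randomization may have caused the event, and a pre-existing lesion would fail that test. The DSMB is also asked to weigh benefit. This lowers the chance of misreading, but grading labels an entry without taking it off the log, and nothing says unrelated entries are left out of the summaries.
- **The AE definition is broad.** It covers any abnormal sign or disease process, related or not, so one cannot say that an incidental lesion plainly falls outside it. The imbalance is the same either way.
- **New findings may be few.** Transthoracic echocardiography and catheterization within a year, EF of at least 50%, and exclusion of moderate or greater valve disease should lower f, though not to zero.

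A reader might also infer that list items d (unplanned CABG revision) and e ("Unplanned open valve repair or replacement") count TEE-prompted changes of plan as default-arm harm, because neither is limited to after surgery. That reading is not established. Stroke, tamponade, pneumonia and other items lack the qualifier too, and item (1)b of the same section describes the cardiovascular category as complications after CABG. An SAE must be fatal or life-threatening. Section 11.1 gives the as-needed arm the greater risk of delayed diagnosis, so the net direction for these items is open.

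**Conclusion.** The point holds for incidental scan findings. Followed as written, section 8.6 makes the AE log depend on how often each arm is scanned, and the expected imbalance is toward the default arm. Its size is unknown: about 2 entries at 22 per arm, or about 1 at 11 per arm, with f and q both assumed at 10% and equal finding rates among scanned patients. It is smaller if as-needed scans are done for cause, and can reach zero at the extreme.

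A reader might take the ratio of entries to be exactly 1/q (10:1 at q=10%) whatever the finding rate. That needs equal finding rates among scanned patients, which the documents do not support when as-needed TEE is done on request or for medical necessity.

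The effect is confined to the AE summaries, the logs sent to the DSMB, IRB and NHLBI, and any reading of them by arm. Both primary endpoints and the four clinical outcomes are untouched. It should be corrected, but it does not threaten the feasibility conclusions.

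**What to change.** - In section 8.6, have incidental scan findings recorded on a separate incidental-findings form, or as a flagged category, giving the arm, the finding and whether it changed the operation. Keep sending them to the DSMB and leave the referral sentence unchanged.
- State that these records are excluded from AE counts that are summarized or compared by arm, and are reported by arm as their own item.
- Reconcile section 8.6 with section 19.1.1.1: the tracked list does not name incidental findings, and the AE definition points to subsection 5 for a list that stands at item (3).
- Do not take index-operation events out of items d and e. Restricting them to after the operating room would drop intraoperative revisions in both arms, including any tied to the delayed-diagnosis risk in section 11.1. At most, record whether each such event was intraoperative or post-surgical and whether TEE preceded it.

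The cost is a wording change, one short form and a lower total AE count. In return the trial obtains a by-arm record of what TEE found and whether it changed surgery.

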8.7 Study Termination

- This study may be suspended or terminated at any time by the will of the NIH, NHLBI, UPenn IRB, or the FDA.

Clinical Study Number:	NCT06154265	Document Title:	10/24/2024	Page 17 of 36
		Default vs As-Needed Intraoperative Transesophageal Echocardiography (TEE) in Low-Risk Isolated Coronary Artery Bypass Graft (CABG) Surgery: A Randomized Controlled Trial		

9 Sites

This is a single site study being conducted at Penn Presbyterian Medical Center (PPMC), a site within the University of Pennsylvania Health System.

10 Data Management and Statistical Analysis Plan

The study data will be captured on Case Report Forms (CRF), as appropriate. The study data, including adverse events, will be summarized for final reports to NHLBI and the NIH. Only staff delegated by the PI ([name]) will have access to the data.

10.1 Primary Endpoint Analysis

The goal of this RCT is to assess the real-world feasibility of undertaking a trial that will randomize isolated CABG surgery patients to default (i.e. obligatory) as-needed (i.e. backup) intraoperative TEE. Therefore, primary RCT endpoints are process-related. These include

1. Absolute subject recruitment
2. Number of TEEs performed in the as-needed TEE trial arm

10.2 Secondary Endpoint Analysis

Although this study is not powered to detect a difference in clinical outcomes between the default and as-needed intraoperative TEE groups, to plan for a future RCT that would be powered to detect a difference in clinical outcomes. We will collect clinical data on gastroesophageal dysfunction (symptoms or injury), incidence of end-organ dysfunction, and incidence of death as defined by the following:

1. Evidence of clinically-significant gastroesophageal dysfunction during hospitalization – either by patient-reported symptoms or by the presence of testing for swallowing difficulty, dysfunction, or upper endoscopy diagnostic procedures.
2. Evidence of end-organ dysfunction based on clinical notes (e.g. “transaminitis,” “acute kidney/renal injury”), and/or laboratory-based evidence of (e.g. liver function tests [LFTs], serum creatinine [Cr], lactate, etc.).
3. Incidence of in-hospital, post-surgical, cardiovascular re-intervention (e.g. return to the operating room for any reason, unplanned or emergency cardiac catheterization post-surgery, or placement on venoarterial extracorporeal membrane oxygenation [VAECMO]).
4. Incidence of all-cause in-hospital mortality

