Secondary Objectives	
Secondary Objectives:
 
 1. Evidence of clinically-significant gastroesophageal dysfunction during hospitalization – either by patient-reported symptoms or by the presence of testing for swallowing difficulty, dysfunction, or upper endoscopy diagnostic procedures. 2. Evidence of end-organ dysfunction based on clinical notes (e.g. “transaminitis,” “acute kidney/renal injury”), and/or laboratory-based evidence of (e.g. liver function tests [LFTs], serum creatinine [Cr], lactate, etc.). 3. Incidence of in-hospital, post-surgical, cardiovascular re-intervention (e.g. return to the operating room for any reason, unplanned or emergency cardiac catheterization post-surgery, or placement on venoarterial extracorporeal membrane oxygenation [VAECMO]). 4. Incidence of all-cause in-hospital mortality
Population	Isolated CABG surgery patients meeting trial eligibility criteria (see inclusion/exclusion), scheduled to undergo surgery at hospitals within the University of Pennsylvania Health System.
Key Eligibility Criteria	In addition to meeting strict inclusion and exclusion criteria, subjects must be willing and capable of providing informed consent and physically capable of performing study related activities.
Site	Hospitals within the University of Pennsylvania Health System

Clinical Study Number:	NCT06154265	Document Title:	10/24/2024	Page 7 of 36
		Default vs As-Needed Intraoperative Transesophageal Echocardiography (TEE) in Low-Risk Isolated Coronary Artery Bypass Graft (CABG) Surgery: A Randomized Controlled Trial		

Study Duration	24 months
Participant Duration	
Active participations: Informed consent duration: approximately 30 – 60 minutes
 
Study duration: 5 days (120 hours) starting with the time of patient enters the cardiac operating room for CABG surgery.
 
Passive participation: Full study duration for the purposes of data acquisition, data cleaning, report generation, manuscript preparation and publication where applicable.
 
Total time: ~24 months

Clinical Study Number:	NCT06154265	Document Title:	10/24/2024	Page 8 of 36
		Default vs As-Needed Intraoperative Transesophageal Echocardiography (TEE) in Low-Risk Isolated Coronary Artery Bypass Graft (CABG) Surgery: A Randomized Controlled Trial		

4 Background Information

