8.3 Randomization and Trial Protocol

8.4.1 Randomization

- Randomization will occur on the day of surgery after placement of an arterial line for invasive hemodynamic monitoring (routine for all patients undergoing isolated CABG surgery) and following induction of anesthesia and successful placement of the endotracheal tube. This will ensure that any patient who is hemodynamically unstable (defined by the exclusion criteria listed above) following induction of anesthesia is excluded from the trial (and will receive an obligatory intraoperative TEE).

Clinical Study Number:	NCT06154265	Document Title:	10/24/2024	Page 15 of 36
		Default vs As-Needed Intraoperative Transesophageal Echocardiography (TEE) in Low-Risk Isolated Coronary Artery Bypass Graft (CABG) Surgery: A Randomized Controlled Trial		

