8.4 Data Collection

8.5.1 Electronic Medical Record (EMR) Data Collection

- The PI ([name]) or other IRB-approved research personnel will collect post-surgical, clinical information from the electronic medical record, pre-surgically, and up to 5 days post-surgery. All data will be collected and securely stored on RedCap or on a single, password-protected, UPenn-regulated, laptop owned by the PI ([name]). No paper records will be kept.

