11.1 Risks Associated with Trial Participation

- The following risks are inherent to participation in this RCT:
 - (1) Risk of gastroesophageal harm from the TEE probe itself: Patients in the default TEE treatment arm will be exposed to, (patients in the as-needed TEE treatment arm may be exposed to) the gastroesophageal clinical risks associated TEE. Patients in the as-needed TEE treatment arm may be exposed to the gastroesophageal clinical risks associated with the use of The current cardiac surgery literature indicates that the risk of clinically significant gastroesophageal injury ranges 0.1% – 4%.¹⁷⁻²⁰ On balance, patients randomized to the default TEE trial arm will have a greater risk of gastroesophageal injury than patients randomized to the as-needed TEE trial arm.
 - (2) Risk of harm from the absence of continuous TEE monitoring during isolated CABG surgery: Patients randomized to the as-needed intraoperative TEE arm may be exposed to potential negative consequences associated with delayed diagnoses of hemodynamic instability. For instance, if EKG changes are detected intraoperatively and a TEE is deemed necessary (by the cardiac surgeon or cardiac anesthesiologist) to investigate for potential regional wall motion abnormalities caused by graft ischemia, confirmation of the diagnosis by TEE may take minutes in the as-needed TEE treatment arm (vs. seconds in the default TEE treatment arm). On balance, patients randomized to the as-needed trial arm will have greater risk of delayed diagnosis than patients randomized to the default TEE trial arm.
 - (3) Loss of time: Participating in the trial will require patients to spend additional time above and beyond the typical perioperative timeframe for undergoing an isolated CABG surgery to review trial-related information, consider the risks associated with participation in the trial (i.e. informed consent process), and answer trial-related questionnaires after surgery.
 - (4) Loss of privacy and confidentiality: Although the risk of occurrence is unlikely, there is a risk of inadvertent disclosure of protected health information (PHI),

Clinical Study Number:	NCT06154265	Document Title:	10/24/2024	Page 19 of 36
		Default vs As-Needed Intraoperative Transesophageal Echocardiography (TEE) in Low-Risk Isolated Coronary Artery Bypass Graft (CABG) Surgery: A Randomized Controlled Trial		

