15.1 Source Data

Source data for this study will include:

- Protected Health Information (PHI) including: (1) name; (2) medical record number (MRN); (3) date of surgery

Electronic medical record (EMR) clinical data including: (1) medical and surgical history; (2) presurgical data and imaging (e.g. laboratory values, cardiac catheterization, transthoracic or transesophageal echocardiography, etc.); (3) intraoperative hemodynamic data (e.g. intraoperative blood pressure, pulmonary

Clinical Study Number:	NCT06154265	Document Title:	10/24/2024	Page 23 of 36
		Default vs As-Needed Intraoperative Transesophageal Echocardiography (TEE) in Low-Risk Isolated Coronary Artery Bypass Graft (CABG) Surgery: A Randomized Controlled Trial		

arterial pressure, mixed venous oxygen saturation, type and dose of intotropes, etc.); (4) postsurgical data and imaging (e.g. postsurgical care notes, laboratory values, imaging, etc.)

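### Secondary endpoint 3 counts only post-surgical re-intervention and no endpoint records diagnostic delay, although the randomized strategies differ during the operation

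*Combined protocol and SAP*

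**What the plan says.** **Timing of randomization.** Section 8.4.1 randomizes on the day of surgery, "following induction of anesthesia and successful placement of the endotracheal tube". Sections 8.4.2 and 8.4.3 then separate the arms by whether the probe is placed at that point or held in the room until someone asks for it.

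**Named risk.** Section 11.1, item 2, says that "patients randomized to the as-needed trial arm will have greater risk of delayed diagnosis" than those in the default arm. Its example is suspected graft ischemia, where "confirmation of the diagnosis by TEE may take minutes in the as-needed TEE treatment arm", against seconds in the default arm.

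**Endpoints.** Section 10.2, repeated in the synopsis, lists four secondary endpoints:
- Item 1: "Evidence of clinically-significant gastroesophageal dysfunction during hospitalization".
- Item 2: end-organ dysfunction from notes or laboratory values, with no start time.
- Item 3: "Incidence of in-hospital, post-surgical, cardiovascular re-intervention", with return to the operating room, unplanned catheterization and VAECMO as examples.
- Item 4: in-hospital death from any cause.

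The second primary endpoint (section 10.1) is the number of TEEs performed in the as-needed arm.

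**Data windows.** The synopsis sets active study duration at "5 days (120 hours) starting with the time of patient enters the cardiac operating room for CABG surgery". Section 8.5.1 says that research staff "will collect post-surgical, clinical information from the electronic medical record", both before surgery and up to day 5 afterwards. Section 15.1 includes, as source data item "3) intraoperative hemodynamic data (e.g. intraoperative blood pressure", a group of variables that extends to inotrope type and dose.

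**The concern.** The operation is the period in which the assigned strategies differ, yet the re-intervention endpoint begins when the operation ends. The protocol text shown does not define post-surgical. On its ordinary reading, a randomized patient placed on VAECMO before leaving the operating room is not an event, while the same patient cannulated an hour later in intensive care is.

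The cut-off also falls on a variable that the intervention affects. Item 3 depends on when a problem is detected and acted on, and the timing of detection is what default and as-needed TEE are expected to change. A difference between arms in item 3 could reflect a shift of events across the cut-off rather than a difference in how many occurred.

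Section 10.2 says that the clinical data are collected to plan a powered trial, and section 19.5.1 plans between-arm tests of them. What is at stake is the safety description and the choice of outcomes for that later trial, not a primary result of this one.

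**Working it through.** The plan states no event rate, power or effect size for this endpoint, so there is no figure to reproduce. The main check compares the wording of each endpoint with the time of randomization and the named risk.

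**Step 1. Which endpoints cover the operation?**

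| Endpoint | Window as worded | Covers intraoperative events? | Records delay? |
|---|---|---|---|
| Primary 1, recruitment | not applicable | no | no |
| Primary 2, TEEs in as-needed arm | during surgery | a count of TEEs only | no |
| Secondary 1, gastroesophageal | hospitalization | not relevant to delay | no |
| Secondary 2, end-organ dysfunction | no start stated | downstream injury only | no |
| Secondary 3, re-intervention | post-surgical | no | no |
| Secondary 4, death | in hospital | yes, death in the operating room counts | no |

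One of the four secondary endpoints is restricted to the period after surgery. None of the two primary and four secondary endpoints directly measures diagnostic delay, intraoperative instability, revision before closure or intraoperative mechanical support.

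**Step 2. Does adverse-event reporting fill the gap?** In part. Collection runs from consent (sections 8.6 and 13.1), so it spans the operation. The list in section 19.1.1.1 includes death, stroke, unplanned CABG revision and unplanned open valve repair or replacement without a post-surgery limit. It does not itemize mechanical support, return to bypass or intraoperative instability, and its cardiovascular category is worded as complications after surgery. By contrast, exclusion criterion 14 (section 6.3.2) already names balloon pump, VAECMO and percutaneous support as instability events that exclude a patient before randomization. Once the patient is randomized, no endpoint counts the same events during surgery.

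**Step 3. Which way could the cut-off bias the comparison?**
- A graft problem seen on default TEE and revised before closure is not counted. The same problem found late and treated by return to the operating room is counted. This lowers the default-arm count.
- A problem diagnosed late in the as-needed arm and rescued with mechanical support in the operating room is not counted. This lowers the as-needed count.

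Both are possible, and the documents give nothing from which to sign the net effect.

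**Step 4. Illustration of size, under assumed rates.** Let r be the true re-intervention rate from randomization, f the share occurring before the patient leaves the operating room, and n the number in the arm. The chance of recording at least one event is 1 − (1 − r(1 − f))^n. With n = 22 (section 10.3):

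| r (assumed) | all counted (f = 0) | f = 25% uncounted | f = 50% uncounted |
|---|---|---|---|
| 5% | 1 − 0.95^22 = 67.6% | 1 − 0.9625^22 = 56.9% | 1 − 0.975^22 = 42.7% |
| 10% | 1 − 0.90^22 = 90.2% | 1 − 0.925^22 = 82.0% | 1 − 0.95^22 = 67.6% |

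A zero count is weak evidence in any case. The exact two-sided 95% upper bound for 0 of n is 1 − 0.025^(1/n), which is 15.4% for n = 22. Section 19.5.2 can be read as 22 patients in total; with equal allocation n = 11, and the bound is 28.5%.

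**The case against.** The strongest reply is that harm from missing TEE is a set of consequences, not minutes of delay, and the plan does look for consequences: renal and hepatic injury, lactate, return to the operating room, emergency catheterization, VAECMO and death. Adverse events are collected from consent, graded and assessed for relatedness. Section 15.1 includes intraoperative hemodynamics, section 19.5.1 plans descriptive statistics on perioperative factors by arm, and the span in section 8.5.1 encloses the operation. All of this stands, and it rules out several stronger readings:

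- A reader might infer that every clinical endpoint begins after surgery. Only item 3 does.
- A reader might infer that harm from delayed diagnosis is never measured. Items 2 and 4 and the adverse-event list capture part of it.
- A reader might infer that delayed diagnosis is the main risk of the as-needed arm. Section 11.1 lists it second of four and does not rank them.
- A reader might infer that the gap makes the as-needed strategy look safer. Step 3 shows that the direction is open.

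A second reply is that post-surgical re-intervention is a coherent measure of problems missed in the operating room. Section 4 describes the benefit of TEE in valve surgery in just those terms. In addition, a revision prompted by TEE may be benefit or overtreatment, so adding it to a single count could penalize the default arm. This also stands. It argues against pooling, not against recording intraoperative events.

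A third reply is that this is an unpowered feasibility study. That is correct and limits the weight of the point. But a feasibility study is the place to learn whether the later trial's safety outcomes can be captured, and description needs no power.

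**Conclusion.** The point holds as an inexpensive improvement to one secondary endpoint and to the description of as-needed TEE. Item 3 excludes re-intervention between randomization and leaving the operating room, and its count depends on the timing of detection, so an arm difference in either direction would be hard to interpret. No endpoint records the delay named in section 11.1. Section 8.4.3 keeps the machine and probe in the room to limit that delay, but nothing in the plan checks whether this works. Section 11 justifies participation partly by learning who should have TEE, when and why, yet the as-needed arm yields only a number of TEEs.

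The size cannot be fixed from the documents. Under assumed rates of 5% to 10% with a quarter to half of events intraoperative, the chance of seeing any event among 22 as-needed patients drops by 8 to 25 percentage points (90.2% to 82.0% at the least, 67.6% to 42.7% at the most). The conclusion rests on reading post-surgical in its ordinary sense. Neither primary endpoint is affected.

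**What to change.** 1. In section 10.2, item 3, and the synopsis, start the count at randomization. Report two descriptive lines per arm: intraoperative events (new mechanical circulatory support, return to bypass, graft revision after grafting was complete, unplanned valve or aortic procedure) and post-surgical events as now defined. Do not pool the two lines, and define the boundary between them, for example leaving the operating room.
2. For each TEE in the as-needed arm, record the reason, the time of request and the time of the first stored image. Summarize the delay descriptively, without a test.
3. Reword section 8.5.1 so that the intraoperative record is explicitly collected, in line with section 15.1.

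The cost is a few case report form fields taken from the operative note, the anesthesia record and image time stamps, with slightly more abstraction per patient. No procedure is added. Request times should be captured prospectively, because they may not be recoverable later.
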